2.5.2 Statistical hypothesis, model, and method of analysis

The objective is to demonstrate that either CFZ533 treatment arm is superior to the control arm with respect to mean change in eGFR at 12 months post-transplantation.

The null hypothesis is that the mean change from randomization in eGFR for a CFZ533 treatment arm is not superior to that in the control arm.

The alternative hypothesis is that the mean change from randomization in eGFR for a CFZ533 treatment arm is superior to that in the control arm.

The null hypothesis will be tested at a significance level of 10% against a one-sided alternative hypothesis, and the test statistic will be the estimated treatment difference at Month 12 based on least squares means from either the MMRM to allow for adjustment for correlations between time points within participants or the ANCOVA model in case of convergence issue.

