12.5.2 Safety endpoints

12.5.2.1 Renal function

The key secondary objective is to evaluate renal function (eGFR) at Month 12. GFR will be estimated using the MDRD formula described in Section 16.4.

Central laboratory serum creatinine values will be used for all renal function data analysis. If the central lab value is missing, then the local creatinine value will be used, if available.

The estimand is:

- 1. population: Full analysis set (FAS)
- 2. endpoint: change from randomization in eGFR at 12 months post-transplant
- 3. **intercurrent events**: regardless of missing assessments, discontinuation of study treatment, graft loss, or loss-to-follow-up

4. **summary measure**: the difference in mean eGFR on CFZ533 at 12 months post-transplant as compared to control

The mean change for each arm will be obtained through covariate-adjusted treatment effects using MMRM. The model will contain treatment arm, visit, treatment arm*visit, and randomization GFR with unstructured covariance matrix. The estimand will be evaluated in the FAS population by comparing the difference in mean change between each CFZ533 arm and control.

Renal function at Month 24 measured by eGFR will also be evaluated following the same analyses strategy.

Hypothesis testing

The objective is to demonstrate that either CFZ533 treatment arm is superior to the control arm with respect to mean change in eGFR at 12 months post-transplant.

The null hypothesis: the mean change from randomization in eGFR for a CFZ533 treatment arm is not superior to that in the control arm.

The alternative hypothesis: the mean change from randomization in eGFR for a CFZ533 treatment arm is superior to that in the control arm.

The null hypothesis will be tested at a significance level of 10% against a one-sided alternative hypothesis, and the test statistic will be the estimated difference in Month 12 least squares means from the mixed effects model to allow for adjustment for correlations between time points within participants.

Handling of missing values/censoring/discontinuations

The primary analysis is based on the FAS, i.e., all observations whether on- or off-treatment. Since participants continue to be followed after early study drug discontinuation, the number of missing values is expected to be limited.

- 1. For participants with graft loss or death, a value of 0 will be imputed after the time of graft loss.

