1.1 Study design

This study is a 12-month, multicenter, open-label, randomized study with a 12-month additional follow-up and a long-term extension that will consist of:

- A screening period (up to 2 months) starting from informed consent, screening visit, and including successful liver transplantation (LTx).
- Run-in treatment period following the successful transplantation that ends on the day of randomization or randomization failure, at Day 8 (with visit window of ±2 days) post-LTx.
- The primary treatment period (Treatment Period 1) starting at randomization Day 8±2 post-LTx up to Month 12 followed by a 12-month follow-up treatment period (Treatment Period 2) until Month 24 (Figure 1-1).
- The long-term extension period (Treatment Period 3) starting post Month 24 until the end of the study (EOS).

Participants will be consented and screened for eligibility prior to liver transplantation. Consented participants who have met the screening inclusion criteria, undergone a successful liver transplantation and been initiated on a tacrolimus-based regimen that includes mycophenolate mofetil (MMF) and corticosteroids (CS) according to local practice, will enter the run-in period. Transplanted participants who meet the additional inclusion criteria will be randomized at Day 8 ± 2 post-LTx.

At least 128 participants will be randomized at a ratio of 2:3:3 to TAC Control (Arm 1) or one of two maintenance regimens of CFZ533: 600 mg CFZ533 subcutaneous (SC) injections every 2 weeks (Arm 2) or 300 mg CFZ533 SC injections every 2 weeks (Arm 3) combined with MMF and CS (Figure 1-1).

Each CFZ533 arm will have a loading period where CFZ533 will be administered IV in order to rapidly achieve concentrations providing complete CD40-CD40L pathway blockade in target tissues in conditions where CD40 expression levels may be enhanced (Section 4.2 in the Protocol for dose rationale). Participants who do not meet the randomization criteria will be designated screen failures. The screen-failed participants will not be further followed-up in the study.

The study treatments will be as follows:

- Arm 1 (TAC Control): TAC, MMF, and CS will be started in the peri-transplant period and at randomization and will continue up to EOS. Initial tacrolimus target trough levels will be between 5 15 ng/mL based on b.i.d. dosing and will be maintained throughout the run-in period. From randomization onwards, the TAC levels will be adjusted as per local label.

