2.5 Analysis of the key secondary objective

2.5.1 Key secondary endpoint

The key secondary objective is to evaluate renal function (eGFR) at Month 12. GFR will be estimated using the MDRD formula (Levey et al 2006):

$$GFR [mL/min/1.73m^{2}] = 175 * (C^{-1.154}) * (A^{-0.203}) * G * R,$$

where

C is the serum concentration of creatinine [mg/dL],

A is age [years],

G = 0.742 when gender is **female**, otherwise G = 1, and

R = 1.212 when race is **black**, otherwise R = 1.

Central laboratory serum creatinine values will be used for all renal function data analysis. Summary statistics for central eGFR change from randomization will be produced.

The estimand is:

- Population: defined through appropriate inclusion/exclusion criteria to reflect the targeted population.
- Endpoint: change from randomization in eGFR at 12 months post-transplant
- Treatment of interest: the randomized treatment, CFZ533 300mg + MMF, and CFZ533 600mg + MMF, TAC+MMF, regardless of treatment or study discontinuation, loss to follow-up, ascites-based dosing adjustment, or administration of CS (treatment policy).
- Summary measure: the difference in mean eGFR on CFZ533 arms at 12 months posttransplantation as compared to control.

The mean change for each arm will be obtained through covariate-adjusted treatment effects using MMRM where visit is treated as a categorical variable. The model will contain treatment arm, visit, treatment arm*visit interaction, and eGFR at randomization with unstructured covariance matrix. In case of a convergence issue with the MMRM model, Compound Symmetry structure will be used for the covariance matrix. If convergence issue still persists,

Novartis	For business use only	Page 24
SAP		CCFZ533A2202

an ANCOVA model will be used for Month 12 visit. The estimand will be evaluated in the FAS population by comparing the difference in mean change between each CFZ533 arm and control.

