3.3 Power for key secondary variable

The primary analysis of renal function is based on the FAS. Participants continue to be followed after study drug discontinuation and participants with graft loss or death will have their Month 12 values imputed as described in Section 2.5.3. For treatment comparisons, there will be a

Novartis	For business use only	Page 35
SAP		CCFZ533A2202

randomized sample of 48 and 32 participants in the CFZ533 and control arms respectively after 12 months. Assuming a common standard deviation of 16 mL/min and one-sided $\alpha = 0.10$, there is 63, 73, or 81% power to detect a difference of 6, 7, or 8 mL/min/1.73m² respectively. If the standard deviation is 20, there is 51, 59, or 67% power respectively. The power calcuation is completed by nQuery 8.4 based on two-sample *t*-test with equal variance.

4 Change to protocol specified analyses

Not applicable.

5 Appendix

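### The key secondary eGFR objective is to show that either CFZ533 arm is superior, but the one-sided 10% level belongs to each arm's test; for the either-arm claim the false-positive chance is about 16% if neither dose has an effect

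*SAP*

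**What the plan says.** SAP 2.5.2 gives the objective as a single statement covering two doses: "The objective is to demonstrate that either CFZ533 treatment arm is superior to the control arm with respect to mean change in eGFR". Protocol 12.5.2.1 has the same wording: "The objective is to demonstrate that either CFZ533 treatment arm is superior to the control arm".

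The null hypothesis is written for one arm at a time: "the mean change from randomization in eGFR for a CFZ533 treatment arm is not superior to that in the control arm". The level follows: "The null hypothesis will be tested at a significance level of 10% against a one-sided alternative hypothesis". SAP 2.5.1 confirms that there are two contrasts from one model, "comparing the difference in mean change between each CFZ533 arm and control".

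SAP 3.3 (and Protocol 12.7) bases power on a "randomized sample of 48 and 32 participants in the CFZ533 and control arms respectively", with the assumption "Assuming a common standard deviation of 16 mL/min and one-sided" alpha of 0.10. It gives 63, 73 and 81% power for differences of 6, 7 and 8 mL/min/1.73m² at SD 16, and 51, 59 and 67% at SD 20.

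For this test neither document has an alpha split, an order of doses, a Dunnett or Hochberg step, a gate from the primary endpoint, an exploratory label, or a statement that multiplicity is deliberately left uncontrolled.

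**The concern.** The objective is met if either of two tests rejects, and each test has the full 10% to spend. The level printed beside the objective is therefore the error rate of a component test, and the claim attached to it has a higher one. A reader of the report who sees superiority shown for one arm at one-sided 10% would naturally take 10% as the error rate of that claim.

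This matters more than usual here because it is the only formal hypothesis test I find in the current SAP. The primary endpoint is judged by a posterior probability (SAP 2.4.2), and the secondary efficacy analyses have been removed (SAP 2.6). Better renal function is also the main benefit that the protocol's rationale puts forward for replacing calcineurin inhibitors.

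**Working it through.** **Inputs.** Arm sizes are 48, 48 and 32 (SAP 3.3), which match the randomization ratio: "At least 128 participants will be randomized at a ratio of 2:3:3 to TAC Control". The level is one-sided 0.10 (SAP 2.5.2). The SD is 16 or 20 and the differences are 6, 7 and 8 (SAP 3.3).

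**Step 1: reproduce the stated power.** The standard error of one contrast at SD 16 is 16 × √(1/32 + 1/48) = 16 × 0.2282 = 3.65. The noncentrality for 6 mL/min is 6/3.65 = 1.64. A two-sample t-test with 48 + 32 − 2 = 78 degrees of freedom at one-sided 0.10 gives:

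| Difference (mL/min) | SD 16: recomputed (stated) | SD 20: recomputed (stated) |
|---|---|---|
| 6 | 63.8% (63) | 51.0% (51) |
| 7 | 73.4% (73) | 59.6% (59) |
| 8 | 81.5% (81) | 67.8% (67) |

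The stated figures reproduce, apparently truncated, as one unadjusted comparison. A two-sided 10% test does not fit: at SD 16 it gives 50, 61 and 71%. The full one-sided 10% is therefore spent on each arm.

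**Step 2: correlation of the two tests.** Both contrasts share the control mean. With equal variances,

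ρ = (1/32) / (1/32 + 1/48) = 48/(48 + 32) = 0.60.

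This depends only on the allocation ratio, not on the SD or the total sample size.

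**Step 3: chance of at least one false claim when neither dose has an effect.** With critical value 1.2816 for each test,

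1 − P(Z₁ < 1.2816, Z₂ < 1.2816 | ρ = 0.60) = 1 − 0.839 = 0.161.

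A simulation of 2 million trials using pooled t statistics (125 degrees of freedom) also gives 16.1%. Nearby correlations change little: 16.8% at ρ = 0.5 and 15.3% at ρ = 0.7. Independent tests would give 1 − 0.9² = 19.0%.

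**Step 4: boundary that would hold the either-arm claim at 10%.** Solving the Step 3 expression for 0.10 gives z = 1.556, a nominal one-sided p of 0.060. The interval where the two standards disagree is thus a better-arm p between 0.060 and 0.10.

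**Step 5: what that boundary costs (SD 16).**

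| Difference (mL/min) | One arm, p ≤ 0.10 | One arm, p ≤ 0.060 | At least one arm if both work, unadjusted | At least one arm if both work, Dunnett |
|---|---|---|---|---|
| 6 | 63.8% | 53.0% | 77.9% | 68.2% |
| 7 | 73.4% | 63.5% | 85.6% | 77.9% |
| 8 | 81.5% | 73.2% | 91.3% | 85.6% |

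The one-arm columns use the noncentral t with 78 degrees of freedom. The last two columns use the bivariate normal with ρ = 0.60.

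**The case against.** The strongest reply is that 10% is the level of each arm's test, that the null is worded for one arm, and that no family-wise rate is promised anywhere. This stands. A reader might infer that the plan states a 10% family-wise rate and gets it wrong, but the documents contain no such figure and no number in the plan is miscalculated. What remains is a mismatch between a per-arm level and an either-arm objective.

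A reader might also take 16% as the general false-claim rate. It is not. It applies when both arms have no effect. If one dose truly works, an error can come only from the other arm, at no more than 10%.

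A third tempting step is to count Month 24 as two further tests, because Protocol 12.5.2.1 says renal function then will be evaluated with the same strategy. The hypothesis text is limited to Month 12 and the SAP's key secondary section covers Month 12 only, so the documents do not support that count. Nor are the power figures ambiguous: 48 versus 32 in a two-sample t-test is plainly one arm against control.

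On consequence, this is an open-label Phase II dose-finding study with a lenient level, and the primary criterion is also applied arm by arm without adjustment. The study was terminated in September 2022 after the interim analysis, and only an abbreviated report follows (SAP 1). The current SAP was therefore written after that analysis, and a Dunnett rule added now would not be true pre-specification. These points carry weight: they make adjustment a debatable choice and labelling the natural first remedy. They do not remove the point. The post-termination SAP kept both the test and the wording about demonstrating superiority, and it nowhere says that multiplicity is waived.

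**Conclusion.** The concern holds as a mismatch between claim and error rate. The one-sided 10% describes each arm's comparison. The either-arm superiority claim has a false-positive chance of about 16% (16.1%, or 1.6 times the per-arm level) when neither dose has an effect. The figure assumes 2:3:3 allocation, a common variance, and Month 12 information roughly in proportion to arm size; correlations of 0.5 to 0.7 keep it between 16.8% and 15.3%. A smaller final sample leaves it essentially unchanged while the ratio holds. The practical effect is confined to a better arm with nominal one-sided p between 0.06 and 0.10. The point limits what may be claimed from this test and does not undermine the eGFR estimates or their intervals. Given the early termination its consequence is modest, but the correction is nearly free.

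**What to change.** **Preferred.** In SAP 2.5.2, replace the objective of demonstrating superiority of either arm with two separate comparisons (600 mg versus control and 300 mg versus control). Describe each as tested at one-sided 10%, unadjusted and exploratory. Add one sentence saying that, with a shared control and 2:3:3 allocation, the chance of at least one false-positive result is about 16% if neither arm has an effect. This costs a few sentences, no new analysis and no power. Protocol 12.5.2.1 has the same wording, so the departure can be recorded in SAP Section 4, which now reports no changes from the protocol.

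**If the sponsor wants to keep the either-arm superiority claim at 10%.** Use a step-down Dunnett test on the two contrasts from the same model. The better arm must reach nominal one-sided p ≤ 0.060, and only then is the other arm tested at 0.10. Single-arm power at the first step falls to about 53/64/73% from the stated 63/73/81% for 6/7/8 mL/min at SD 16. Power to show at least one arm superior, if both work, is about 68/78/86%. The report should say that the rule was added after the interim analysis.

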2.5.3 Handling of missing values/censoring/discontinuations

The primary analysis is based on the FAS. Since participants continue to be followed after early study drug discontinuation, the number of missing values is expected to be limited. In case of missing values,

- 1. For participants with death, a value of 0 will be imputed after the time of death.
- 2. Participants that are lost to follow-up or have missing assessments will have missing values assessed via MMRM assuming MAR.

2.5.4 Supplementary analyses

The analysis of eGFR (MDRD-4) will be repeated with assessments occurring after discontinuation of study medication counting as missing in the MMRM model (an "on-treatment" analysis).

2.6 Analysis of secondary efficacy objectives

Not applicable as this is removed from the abbreviated CSR.

2.7 Safety analyses

The SAF will be used for safety analyses unless otherwise specified. General safety summaries (tables, figures, etc.) will include only data from the on-treatment period with the exception of baseline data which will also be summarized where appropriate (e.g., change from baseline summaries), unless otherwise specified. For CFZ533 arms, the on-treatment period lasts from the date of first administration of study treatment to 14 days after the date of the last actual administration. For the Control arm, it lasts to the day of the last actual administration of TAC.

Adverse events (AEs) will be presented and summarized for all treatment-emergent events, with a start date after randomization and covering until 14 weeks after the last administration of CFZ533 for CFZ533 arms and 12 weeks after that of TAC for TAC arm. In addition, a separate summary for death will be provided. Malignancies are summarized under SAEs.

All information obtained on adverse events will be displayed by treatment group. The number and percentage of participants with treatment-emergent adverse events and serious adverse events (events started after the first dose of study medication or events present prior to start of treatment but increased in severity based on preferred term) will be summarized in the following ways:

- by treatment, primary system organ class and/or preferred term
- by treatment, primary system organ class, preferred term and/or maximum severity

Separate summaries will be provided for AEs leading to treatment discontinuation.

In addition, the proportion of participants with infections will be summarized as follows:

- Infections by type of infection (viral, fungal, bacterial, others) and severity.
- Serious infections by type of infection (viral, fungal, bacterial, others) and severity.

The incidence rate of infection by type (viral, bacterial, fungal, and others) will be tabulated for each treatment arm. The key safety parameter is serious infections. The number of serious infections will be used to evaluate the stopping rule as outlined in Section 9.1.5 in Protocol.

Data collected on AE CRFs will be coded with the MedDRA dictionary that gives preferred term (PT) and system organ class (SOC) information. AEs and infections data will be analyzed as a whole under the heading of AEs for each treatment arm. If a participant has multiple occurrences of an AE, the participant will only be counted once in the corresponding AE category. If participant has multiple AEs within a SOC, the participant will be counted only once for that SOC. If a participant has multiple severity ratings for an AE, the participant will be counted under the maximum rating.

Incidence rates of safety topics of interests from eCRS will be summarized by risk categories. Safety topics of interests are defined in Table 2-2.

Safety topics of interests	Search strategy	
Infections	MedDRA search strategy SOC "Infections and infestations" [10021881] and HLGT "Microbiology and serology investigations" [10027529].	
Malignancies including Lymphoproliferative disorder	SMQ Malignant or unspecified tumours (Narrow) (20000091), SMQ Malignancy related therapeutic and diagnostic procedures (20000093) and SMQ Tumour markers (20000094)	
Thrombosis	MedDRA search strategy SMQ "Embolic and thrombotic events (SMQ)" [20000081] and HLT "Coagulation and bleeding analyses" [10009728].	

 Table 2-2
 Safety topics of interests

Novartis	
SAP	

Immunogenicity	PT: Drug specific antibody present [10013745]		
	SMQ: Hypersensitivity (Narrow), (20000214)		
Vaccination failure	Therapeutic product ineffective (10060769)		
	Therapeutic response changed (10074941)		
	Therapeutic response decreased (10043414)		
	Therapeutic response delayed (10053181)		
	Therapy non-responder (10051082)		
	Antibody test abnormal (10061425)		
	Antibody test negative (10061426)		
	Immunology test abnormal (10061214)		
	Vaccination failure (10046862)		
	Vaccine breakthrough infection (10067923)		
	Absence of immediate treatment response (10081766)		
	Drug effect less than expected (10083365)		

The AE, SAE, infections, and serious infections summarized as above will also be provided in corresponding listings.

New onset of diabetes mellitus (NODM)

New onset diabetes mellitus is defined as:

- a. All of the following should be true (no diabetes pre-transplantation):
 - 1. Diabetes was not included in the medical history.
 - 2. Glucose (random) < 11.1 mmol/L (200 mg/dL) at the time of transplantation.
 - 3. Diabetes was not recorded as reason for any medication given prior to transplantation.
 - 4. HbA1c < 5.7% at the time of transplantation
 - 5. If any of the above criteria is unknown (e.g. lab values), the participant will be considered to have no diabetes pre-transplant if all other criteria are true;

AND

- b. At least one of the following should be true (diabetes onset after transplantation):
 - 1. Two consecutive fasting plasma glucose (FPG) \geq 126 mg/dL (7.0 mmol/L) any day after Day 29 or a random plasma glucose (RPG) \geq 200 mg/dL (11.1 mmol/L).
 - 2. HbA1c \geq 6.5% (only from Day 85 onward).
 - 3. Diabetes reported as an AE that is prevalent after Day 29.
 - 4. Any concomitant medication with ATC level 2 code "A10" (drugs used in diabetes), if prevalent after Day 29. Here "prevalent after Day 29" means the described drug has been consecutively used for at least 30 days since Day 29.

Note that participants with steroid-induced diabetes are excluded. The date of onset is the earliest date when any of the conditions in Criterion b above is met. The proportion of participants developing new onset diabetes mellitus (NODM) after transplantation will be summarized by treatment group. Death, graft loss, or loss to follow up without NODM before Month 12 will not be counted as developing NODM. This analysis will be performed using

participants in the FAS population who do not have diabetes mellitus at the time of transplantation according to Criterion a.

Disclosure reporting

For the legal requirements of ClinicalTrials.gov and EudraCT, two required tables on treatmentemergent adverse events which are not serious adverse events with an incidence greater than 5% and on treatment emergent serious adverse events and SAE suspected to be related to study treatment will be provided by treatment, system organ class and preferred term on the SAF.

If for a participant, several consecutive AEs (irrespective of study treatment causality, seriousness and severity) occurred with the same SOC and PT:

- a single occurrence will be counted if there is ≤ 1 day gap between the end date of the preceding AE and the start date of the consecutive AE
- more than one occurrence will be counted if there is > 1 day gap between the end date of the preceding AE and the start date of the consecutive AE

For occurrence, the presence of at least one SAE / SAE suspected to be related to study treatment / non SAE has to be checked in a block e.g., among AE's in a ≤ 1 day gap block, if at least one SAE is occurring, then one occurrence is calculated for that SAE.

The number of deaths resulting from SAEs suspected to be related to study treatment and SAEs irrespective of study treatment relationship will be provided by SOC and PT.

